8.0 Scientific Considerations	
☐ Phase I ☐ Phase II ☐ Phase III ☑ Phase IV	
7.2 If this is a clinical trial, check the applicable phase(s) (Help Text updated 9/13):	
would give two curves from time of insertion to time of CT scan showing penetration. The log rank statistic would look at comparisons over time. Finally, we will also do an analysis of struts counting penetration as one or more and use the total number of penetrating struts as a secondary analysis.	
A correlation test will be performed as well as a survival analysis where a failure is penetration. This	
For sample size, we determined that with \sim 75 patients per group and similar differences in incidence or penetration as our preliminary study (25) (22% & 10%) we will see a significant difference at the p = 0.05 level with power 80%. If the difference is a little wider (25% vs. 10%) we will see significance at 50 patients per group. This calculation is using a comparison of proportions test with a z-statistic.	
IVC filter penetration (defined as greater than 3mm) through the IVC wall be the primary complication we will be measuring.	
Statistical and Power Analysis	

|--|

This study has a hypothesis:

If yes, state the hypothesis or hypotheses:

We hypothesize that there is no significant difference in efficacy and complication rate between the Option and the Denali filter.

8.2 * List the specific aims:

- 1) Determine if there is any difference in filter tilt in the vena cava
- 2) Determine if there is any difference in caval penetration
- 3) Determine if there is any difference in physician satisfaction after filter deployment

8.3 Statistical analysis:

Statistical and Power Analysis

IVC filter penetration (defined as greater than 3mm) through the IVC wall be the primary complication we will be measuring.

For sample size, we determined that with \sim 75 patients per group and similar differences in incidence or penetration as our preliminary study (25) (22% & 10%) we will see a significant difference at the p = 0.05level with power 80%. If the difference is a little wider (25% vs. 10%) we will see significance at 50 patients per group. This calculation is using a comparison of proportions test with a z-statistic.

A correlation test will be performed as well as a survival analysis where a failure is penetration. This would give two curves from time of insertion to time of CT scan showing penetration. The log rank statistic would look at comparisons over time.	

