Finally, we will also do an analysis of struts counting penetration as one or more and use the total number of penetrating struts as a secondary analysis.	
8.4 If this study has undergone scientific or scholarly review, please indicate which entity perform review:	ed the
☐ Cancer Center Protocol Review Committee (PRC) (Full approval is required prior to final CHR approval for cancer-related protocols.)	
☐ CTSI Clinical Research Center (CRC) advisory committee	
▼ Departmental scientific review	
☐ Other:	
Specify Other:	

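### No primary test is named for penetration: the trial is sized on a two-proportion z-test, but the analysis text commits to a log-rank comparison and an undefined correlation test

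*Combined protocol and SAP*

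**What the plan says.** Section 8.3, repeated in section 14.1, identifies the endpoint: "IVC filter penetration (defined as greater than 3mm) through the IVC wall be the primary complication we will be measuring". The sample-size paragraph follows. It takes 22% versus 10% from the department's retrospective study and states that with about 75 patients per group "we will see a significant difference at the p = 0.05 level with power 80" per cent. It closes with "This calculation is using a comparison of proportions test with a z-statistic". That sentence describes the calculation, and it is the only place where the z-test is mentioned. Section 10.4 repeats it.

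The analysis sentences come next: "A correlation test will be performed as well as a survival analysis where a failure is penetration". The survival analysis runs from insertion to the CT that shows penetration, and "The log rank statistic would look at comparisons over time". The last item is to "use the total number of penetrating struts as a secondary analysis".

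The strut count is the only analysis given a rank. Neither section names a primary test, a testing order, a multiplicity rule or the variables in the correlation test. Sidedness is also unstated. The relevant aim in section 8.2 is non-directional: "Determine if there is any difference in caval penetration".

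**The concern.** The z-test and the log-rank test both compare the devices on penetration, but they are not the same test. The z-test ignores how long the filter was in place; the log-rank test depends on it. Dwell time will vary, because section 9.1 has retrieval re-attempted at 30-day intervals until the filter is out, and the same section says complications seem to become more likely over time. The two tests can therefore disagree.

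Two things are at stake. First, with no test designated in advance, the choice could be made after the data are seen, and the 5% level would not then describe the procedure used. Second, even with no selective reporting, a split result would leave the trial without a defined answer to its main question. In addition, the stated power belongs to a test that the analysis text never promises to run.

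**Working it through.** **Inputs from the documents.** 75 per arm; 22% versus 10% (alternative: 25% versus 10% with 50 per arm); level 0.05; power 80%; two-proportion z-test. Two-sided testing is assumed because the aim is non-directional.

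**Step 1: the plan's own figure.** For the pooled z-test,

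n per arm = [1.96·√(2p̄(1−p̄)) + 0.8416·√(p₁(1−p₁)+p₂(1−p₂))]² / (p₁−p₂)²

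- 22% v 10%: p̄ = 0.16; √0.2688 = 0.5185; √0.2616 = 0.5115. n = (1.0162 + 0.4305)² / 0.0144 = 145.3, so 146 per arm.
- 25% v 10%: p̄ = 0.175; √0.28875 = 0.5374; √0.2775 = 0.5268. n = (1.0532 + 0.4434)² / 0.0225 = 99.5, so 100 per arm.

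The stated 75 and 50 per arm are not reproduced. Other versions of the 22% v 10% calculation do not reach 75 either: 143 unpooled, 142 arcsine, 162 with continuity correction, 115 one-sided.

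Power at the stated sizes, Φ{[(p₁−p₂)√n − 1.96·√(2p̄(1−p̄))] / √(p₁(1−p₁)+p₂(1−p₂))}:

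- 75 per arm, 22% v 10%: (1.0392 − 1.0162)/0.5115 = 0.045, power **51.8%** (64.2% one-sided).
- 50 per arm, 25% v 10%: (1.0607 − 1.0532)/0.5268 = 0.014, power **50.6%**.

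**Step 2: choosing the log-rank test would not restore 80%.** Under proportional hazards, HR = ln(0.90)/ln(0.78) = 0.424. Schoenfeld's formula needs 4(1.96+0.8416)²/(ln 0.424)² = 43 events; Freedman's gives 48. Expected events are 75 × (0.22 + 0.10) = 24, for power of about 56%.

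**Step 3: error rate if either test could support a claim.** The documents give no dwell-time distribution, so one must be assumed. Null trials were simulated with 75 per arm, penetration near 16%, and imaging in 30-day steps with different shares imaged at the first visit. Each test used alone rejected in close to 5% of trials.

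| Assumed dwell pattern | z-test or log-rank p < 0.05 |
|---|---|
| 90% imaged at first visit | 5.6%–5.9% |
| 70% at first visit | 6.4%–6.6% |
| 50% at first visit | 6.3%–7.7% |
| long, spread dwell, time-dependent penetration | up to about 8.5% |

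One further set of runs, with three other assumed dwell distributions, gave 7.7% to 8.9%. With 4,000 trials and a rate near 8%, the Monte Carlo standard error is √(0.08×0.92/4000) = 0.4 points, so 8.9% is compatible with a ceiling near 8.5%. For two independent tests the rate would be 1 − 0.95² = 9.75%. These two are strongly correlated, which is why the simulated figures are lower.

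**Step 4: disagreement under a real difference.** With about 22% penetration in one arm, HR near 0.42 and 75 per arm, one test was significant and the other not in about 5% to 22% of trials. The upper end comes with spread dwell times.

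**The case against.** The strongest reply is that the plan does point to a lead test. Directly after naming penetration, it ties the 0.05 level to a comparison of proportions and attaches that level to nothing else. Section 9.1 gives the purpose as characterising incidence, time-course and magnitude. The three analyses can be matched to these: proportions for incidence, log-rank for time-course, strut count for magnitude. On that reading the z-test is primary and no error is added. This is a sensible inference and probably close to the intent, but it remains an inference. The analysis sentences never commit to the z-test, and nothing ranks the log-rank test below it.

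Three further parts of the reply stand:

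- A reader might infer that the trial's error rate exceeds 5%. The documents do not support this as a fact, because they nowhere say that a difference may be claimed on whichever test is significant. They do not rule it out either, so the accurate statement is that the 5% is not protected.
- A reader might count the correlation test and the strut count as further chances of a false positive, which gives figures of 9% to 10%. The strut count is already labelled secondary. The correlation test has no stated variables: if it relates penetration to dwell time it does not compare devices, and if it relates penetration to device it essentially repeats the z-test. Neither belongs in the calculation.
- The plan aims for removal from 30 days. If most patients are imaged then, the two tests nearly coincide and the inflation is small.

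**Conclusion.** The point holds as a gap in the plan: the primary endpoint has no designated primary test, and the test used for sizing is not carried into the analysis text. The cost in false positives is modest and conditional. At 75 per arm it is about 5.5% to 8.5% instead of 5%, and only if a claim on either test were accepted. The range rests on assumed dwell times. The second consequence does not depend on selective reporting: in about 5% to 22% of trials with a true difference near the design assumption, the two tests would split and the plan could not say what was found.

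Naming the z-test also exposes a larger problem. At 75 per arm, that test has about 52% power for 22% versus 10% (two-sided assumed), against the stated 80%. Designating a primary test settles which result counts, but it does not repair the sample size.

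**What to change.** In sections 8.3 and 14.1, state that:

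- the primary analysis is the difference between Denali and Option in the proportion of patients with penetration of more than 3 mm, among those with follow-up imaging, by allocated device, using the two-proportion z-test at two-sided 0.05 and reported with a 95% confidence interval;
- the log-rank analysis, the correlation of penetration with dwell time (so defined) and the strut count are supportive and do not change the primary conclusion.

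The denominator needs to be explicit because section 10.4 expects half of the 300 consented patients not to return for imaging. Stating it does not remove any bias from non-return, which needs its own treatment.

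In the same paragraph and in section 10.4, restate the power for the named test: about 52% at 75 per arm for 22% versus 10%, with 146 per arm needed for 80%.

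The wording change costs one paragraph, written before any data are analysed, and needs no extra patients, visits or data. Whether to enlarge the trial is a separate decision.

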9.0 Background

9.1 Background:

Background

The purpose of inferior vena cava (IVC) filters is preventing pulmonary embolism (PE) for patients with thromboembolic disease when standard medical therapy fails or is contraindicated (1). The most common situations for which IVC filters are used are in patients with deep vein thrombosis (DVT) or PE. Although anti-coagulation therapy is the preferred choice of prophylaxis in the setting of thromboembolic disease, many patients cannot take anticoagulants or continue to experience thromboembolism despite anticoagulation. Examples of when patients are considered for IVC filter placement include patients who have had a recent stroke, gastrointestinal bleeding, following severe trauma, and before and after surgery.

First approved for use in the late 1960's and 1970's, IVC filters were initially thought to be safe to leave in patients for life. More recent research and a flurry of lawsuits have shown that permanent placement of IVC filters can lead to a host of known and unknown side effects and complications. The society of interventional radiology (SIR) and the US Food and Drug Association now recommend retrieval of IVC filters as soon as patient's risk for embolism has subsided and when feasible and clinically indicated.

Potential complications of IVC filters include filter fracture, filter migration, and caval thrombosis (2–6). Additionally, filter components may penetrate through the wall of the IVC. This is most commonly seen with conical filters, with reported incidences varying widely by filter type (7–11). The likelihood of these complications also seems to increase over time. Therefore removal should happen as soon as clinically safe.

Use of IVC filters became commonplace after the general clinical belief in their relative safety and efficacy in preventing PE. (28–32). The advent of retrievable IVC filters has further contributed to this trend. Some filters, including the Option and Denali, are FDA approved for safety and efficacy as retrievable filters, or as permanent devices if left in place. Despite these approvals there is a relatively limited understanding of the way IVC filters behave after they are inserted (33, 34).

One type of behavior with potential clinical significance is the interaction between IVC filters and the vena cava over time. A commonly encountered result of this interaction is vena caval perforation by filter components. Filter fragmentation, filter tilt, or complete filter migration can also occur (35–39). Filter fragmentation or migration can place a patient at considerable risk, however, the clinical significance of IVC perforation continues to be debated. There are scattered reports of patients manifesting symptoms such as pancreatitis, severe back and abdominal pain that resolved after filter removal. Unfortunately, large scale analysis connecting IVC filter complication with symptoms has been lacking in the literature.

Accurate characterization of filter-caval interactions in the clinical setting is essential for valid inferences to be drawn regarding IVC filter behavior over time. Abdominal CT imaging and fluoroscopic venography are common modalities used to visualize IVC filters; however, the information gathered through fluoroscopic venography is limited relative to CT imaging. In contrast, abdominal CT reveals IVC filter position and caval thrombus, as well as showing the vena caval lumen, wall and pericaval tissues. Diagnostic

radiologists can play a vital role when viewing Abdominal CT in identifying filter-related issues that may require specialized management.

The purpose of the present study is to characterize the incidence, time-course, and magnitude of complications of two commonly used IVC filters. Patients who present to Interventional Radiology for IVC filter will be randomized to have either a Denali filter or an Option filter placed. Patients will then be contacted 30-days following filter placement to come for filter removal. If it is not clinically safe for a patient to have the filter removed after 30 days, other attempts will be made to schedule for filter removal at 30-day intervals until the filter is removed. The filter placement and filter removal will be performed in the usual fashion according to the standards of our current practice. Upon filter removal, note will be made to potential complications including: filter perforation, filter migration, filter fracture and thrombus within the filter. Another main purpose of the study is to try to increase the numbers of patients who return promptly for filter removal. Many patients continue to have IVC filters in place for far longer than is needed due to poor follow up procedures and lack of tracking due to many patients being referred in from other services.

Little is presently known regarding the complication tendency of the relatively new Denali conical retrievable IVC filter (Cook, Bloomington, Indiana). The Option has been researched more and has been found to have a slightly lower incidence of complications than other conical filters.

In a prospective multicenter study of 100 Option filters, investigators noted one case of penetration among 39 filters assessed during retrieval cavograms (12); however, penetration was not dealt with as a dedicated endpoint. The option studies also did not randomize what filter was used and the data was only examined retrospectively with varying timepoints. The Denali was approved under an FDA "similar device" exemption so has not been subject to systematic long term study. The present study aims to characterize the incidence and time course of penetration and other complications at regular intervals for the Option filter compared with the Denali.

9.2 Preliminary studies:

The department of interventional radiology at UCSF has recently conducted retrospective comparative studies of IVC filter complications, comparing two devices in two separate studies. This research has inspired us to propose a randomized prospective trial to more clearly evaluate the efficacy of two newer IVC filters.

In a comparison between the Option and Gunther Tulip IVC filters, vena cava penetration by one or more strut was found in 17% of all filters imaged by CT. (25) The filter positions of 58 devices were documented on follow up CT examinations for reasons unrelated to filter placement. There was a 10% prevalence of penetration for the Option and 22% for the Gunther Tulip. Due to the small number of filters imaged in each group, no significant statistical difference in prevalence of filter penetration was found. A secondary analysis determined that Gunther Tulip filters showed time-dependent penetration with penetration become more probable with longer indwelling times of the devices.

Since this study was only a retrospective chart review study, patients were not randomized to each group and therefore it was not possible to get large enough numbers in each group. Also patients were not asked to come back at regular intervals for follow up imaging so any subsequent CT images were obtained for other purposes. The present study will improve on this by having larger numbers of randomized patients in each group and routine standard of care follow up imaging at regular intervals until filter removal.

Our department conducted another similar study comparing Gunther Tulip and Celect IVC filters (26). 50 filters (23 Gunther Tulip and 27 Celect) were assessed through retrospective analysis of follow up abdominal CT images obtained for unrelated reasons. The principal significant finding was that the longer the duration of IVC filter placement, the more likely that filter penetration would occur. Perforation through the IVC was observed in 43 out of 50 (86%) filters on CT scans obtained between 1 and 880 days after filter placement. The study also found that there was filter tilt (defined as greater than 15 degrees) in 20 out of 50 filters. Removal of 12 out of 50 filters was attempted and was successful in 11 of 12.

The present study seeks to expand on this as well by taking into account other factors such as filter tilt, filter breakage, penetration into other organs and retrieval success.

9.3 References:

References

- 2. Kinney TB. Update on inferior vena cava filters. J Vasc Interv Radiol 2003; 14:425-440.

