10.0 Sample Size and Eligibility	
10.1 Number of subjects that will be enrolled at UCSF and affiliated institutions:	
150	
10.2 Total number of subjects that will be enrolled at all sites (Help Text updated 9/13):	
150	
10.3 Estimated number of people that you will need to consent and screen here (but not necessaril enroll) to get the needed subjects:	у
300	
10.4 Explain how and why the number of subjects was chosen (Help Text updated 9/13):	
The numbers are based on statistical power analysis and examination of our findings from previous IVC filter retrospective studies done by UCSF interventional radiology. The most recent study showed that one group of filters had 22% penetration and the other had 10% penetration. However, because the numbers in each group were too small, no significant difference in degree of penetration was found. For sample size, we determined that with \sim 75 patients per group and similar differences in incidence or penetration as our preliminary study (25) (22% & 10%) we will see a significant difference at the p = 0.05 level with power 80%. If the difference is a little wider (25% vs. 10%) we will see significance at 50 patients per group. This calculation is using a comparison of proportions test with a z-statistic.	
To make sure this will be feasible, we looked at the total number of IVC filters placed in the previous year at UCSF Mount Zion and UCSF Parnassus. In 2013, 169 IVC filters were placed in patients between the two hospitals. Since this is a standard of care study and no extra time committment will be required, we expect most patients will be consented and agree to be followed in the study. Over a two year proposed study timeline with on average 340 patients receiving IVC filters, we expect to consent about 300 patients in order to get the 100-150 needed to find significant findings. We expect half of the 300 consented patients to be lost to follow up and not return for follow up imaging and retrieval.	
10.5 * Eligible age range(s):	
 □ 0-6 years □ 7-12 years □ 13-17 years ☑ 18+ years 	

1. Patients scheduled for IVC filter placement at UCSF Moffitt, Mount Zion, or Mission Bay Interventional Radiology Service. 2. 18+ 1. Necessity of permanent IVC filter
Necessity of permanent IVC filter
1. Necessity of permanent IVC filter
2. Genetic or physical abnormalities of the inferior vena cava

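### The 80% power claim borrows its 22% penetration rate from a filter that is not in this trial, without saying so, and the plan's own rates give about 52% power at 75 per arm

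*Combined protocol and SAP*

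**What the plan says.** The trial randomises patients to the Denali or the Option filter (Option Elite in 7.1). Penetration of the caval wall by more than 3 mm is the primary complication.

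The power paragraph stands in 8.3, 10.4 and 14.1, and appears also to close 7.1. It assumes "similar differences in incidence or penetration as our preliminary study (25) (22% & 10" per cent) and concludes that with about 75 per group "we will see a significant difference at the p = 0.05 level with power 80" per cent. It adds that 50 per group would be enough for 25% against 10%, and says that the calculation is a z-test of two proportions. It does not say whether the test is one- or two-sided.

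Section 10.4 introduces the rates without naming the devices: "The most recent study showed that one group of filters had 22% penetration and the other had 10% penetration". Section 9.2 identifies them: "There was a 10% prevalence of penetration for the Option and 22% for the Gunther Tulip". It also says how they were obtained: "The filter positions of 58 devices were documented on follow up CT examinations for reasons unrelated to filter placement". Those patients had no scheduled imaging, and the difference was not significant.

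For Denali, 9.1 says that little is known about its complications and gives no penetration rate. On timing in this trial: "Patients will then be contacted 30-days following filter placement to come for filter removal", with further attempts at 30-day intervals and a rotation CT before removal.

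**The concern.** A power statement should describe the comparison that the trial will make. This one contains no information on Denali, and a reader of 8.3, 10.4 or 14.1 alone cannot see that one of the two rates belongs to a third device. The rates also come from unscheduled CTs, whereas this trial reads a CT before retrieval, sought from about day 30. Section 9.2 reports that penetration became more likely with longer dwell for the Gunther Tulip, and again in the Gunther Tulip and Celect study, so the rates may not carry over.

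The hypothesis in 8.1 is that the two filters do not differ significantly. A null result from a trial labelled as having 80% power could be taken as support for that hypothesis. The label therefore has to be right, and here it has neither Denali data nor correct arithmetic behind it.

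**Working it through.** **Inputs.** 75 per arm, 1:1 (10.4; 75 envelopes of each kind in 7.1 and 14.1); 22% and 10% (8.3, 9.2, 10.4); 50 per arm for 25% against 10% (10.4); alpha 0.05. Two-sided is my assumption; one-sided results are shown beside it.

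**1. Reproducing the plan's figure.** For the pooled z-test with n per arm and p̄ = (p1 + p2)/2:

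power = Φ{ [ |p1 − p2|·√n − 1.96·√(2p̄(1 − p̄)) ] / √(p1(1 − p1) + p2(1 − p2)) }

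- 22% against 10%, n = 75: (0.12 × √75 − 1.96 × 0.5185)/0.5115 = (1.0392 − 1.0162)/0.5115 = 0.045, so power is **52%** (64% one-sided).
- 25% against 10%, n = 50: (0.15 × √50 − 1.96 × 0.5374)/0.5268 = (1.0607 − 1.0532)/0.5268 = 0.014, so power is **51%** (63% one-sided).

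For 80% power the same test needs 146 per arm for 22% against 10% (115 one-sided) and 100 per arm for 25% against 10% (79 one-sided). Unpooled variance (143), the arcsine method (142) and a continuity correction (162) do not give 75 either.

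A likely explanation, which the plan does not state: 75 and 50 are about the sizes at which those exact observed differences just reach two-sided p < 0.05 (z = 2.00, p = 0.045; z = 1.97, p = 0.048). That corresponds to about 50% power.

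**2. Precision of the borrowed rates.** The group sizes are not given. The only whole-number split of 58 filters that fits 10%, 22% and the 17% overall is 2/21 for Option and 8/37 for Gunther Tulip (10/58 = 17%). This split is inferred. The exact 95% CIs are 1–30% and 10–38%.

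**3. Power if Denali is not at 22%.** With Option at 10%, 75 per arm, two-sided 5%, and the Denali rate assumed:

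| Denali rate | 15% | 18% | 22% | 25% | 28% |
|---|---|---|---|---|---|
| Power | 15% | 29% | 52% | 68% | 81% |

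**4. Denali rate detectable with 80% power** (the formula in step 1, solved for the Denali rate):

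| Assessed per arm | Option 10% | Option 5% |
|---|---|---|
| 75 | 27.8% | 20.0% |
| 50 | 32.7% | 24.7% |
| 37 | 37.2% | 29.1% |

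Fifty per arm is the lower end of the 100–150 patients that 10.4 says are needed. Thirty-seven applies only if half of the 150 enrolled are lost. The 5% for Option is an assumption to show the range.

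**5. Expected precision.** The 95% CI half-width for the difference, at 22% against 10%, is 1.96·√[(0.22 × 0.78 + 0.10 × 0.90)/n]. This is 0.116 at n = 75 (about 12 points) and 0.142 at n = 50 (about 14 points).

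**The case against.** The best defence is that the plan speaks of differences similar to those in the preliminary study. That is a conditional effect size, not a claim that Denali penetrates at 22%. With no Denali data an effect has to be borrowed from somewhere; the 10% does belong to a trial device; and 9.2 names both devices openly. This stands: the borrowing is legitimate in itself. What remains is that the assumption is neither labelled nor justified where the sample size is set. The arithmetic error in step 1 does not depend on which device supplied the 22%.

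A reader might go further in four ways that the documents do not support.

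- **That 80% holds for Option against Gunther Tulip and fails only for Denali.** It does not hold for that pair either. The shortfall at Option 10% is arithmetic, not a result of the device or of dwell time.
- **That early retrieval lowers the power.** The dwell times of the 58 filters are not given, dwell will vary in this trial too, and the time trend in 9.2 was not reported for Option. The shift cannot be sized. Lower base rates raise the power for a fixed 12-point gap at 75 per arm: 52%, 65% and 75% with Option at 10%, 5% and 2.6%. Power falls sharply only if the 2.2-fold ratio is assumed to persist, and the plan speaks of differences.
- **That 2.6% is the right Option rate.** It comes from "one case of penetration among 39 filters assessed during retrieval cavograms" (exact 95% CI 0.1–13.5%, which includes 10%). Section 9.1 adds that penetration was not a dedicated endpoint there, and calls venography limited relative to CT.
- **That only about 37 per arm will be assessed.** Section 10.4 applies the 50% loss to 300 consented patients, which leaves 50 to 75 per arm. The lower figure follows only if the loss falls on the 150 enrolled.

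**Conclusion.** The point holds, and the power statement is wrong as written. It has two separate defects. First, the 22% is the Gunther Tulip rate, used in 8.3, 10.4 and 14.1 without a label or a reason for applying it to Denali, and both planning rates are imprecise. Second, the stated 80% is not delivered even on those rates: power is 52% at 75 per arm and 51% for the 50-per-arm scenario (64% and 63% one-sided).

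These figures assume a pooled two-proportion z-test, equal arms, and 75 or 50 patients actually assessed per arm. The size of the detectable gap depends on the Option rate: 17.8 points at 10%, 15.0 at 5% and 13.0 at the cavogram figure of 2.6%. The documents therefore do not show that the trial is blind to everything but differences far larger than 12 points. They show that the claimed power is not supported for the comparison being made.

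**What to change.** In 8.3, 10.4 and 14.1 (and in the same paragraph in 7.1):

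- State that 22% is the Gunther Tulip rate, used as an assumed effect size because no Denali rate is available.
- Replace the 80% sentence and the 50-per-group sentence with the correct power, 52% and 51%, and state that the test is two-sided.
- Add the detectable Denali rates at 80% power: 27.8% and 20.0% at 75 assessed per arm, and 32.7% and 24.7% at 50, for Option at 10% and 5%.
- Add the expected 95% CI half-width for the difference: about 12 points at 75 per arm and 14 at 50.
- Show a 2.6% Option row (15.6% detectable at 75 per arm) only if it is labelled as 1/39 on cavograms, 95% CI 0.1–13.5%, with penetration not a dedicated endpoint.
- Label any 37-per-arm row (37.2% and 29.1%) as the case where half of the 150 enrolled are lost.
- Commit to reporting the difference in penetration with its 95% CI, and not to describing a non-significant result as showing no difference.

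The cost is a few sentences and a small table. No extra patients or procedures are needed. The price is that the stated power becomes less favourable.
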